3.4.2 Subject withdrawal

Subjects may withdraw from the study at any time and for any reason without prejudice to their future medical care by the investigator or at the study site. Every effort should be made to keep subjects in the study, including if a subject and/or their treating physician decides to prematurely discontinue study treatment. The reasons for subjects not completing the study will be recorded. A subject may be withdrawn from the study for any of the following reasons:

1. The subject is noncompliant with the protocol.
2. The subject has a serious or intolerable adverse event(s) (AE[s]) that, in the investigator's opinion, require(s) withdrawal from the study.
3. The subject has laboratory safety results that reveal clinically significant hematological or biochemical worsening from the baseline values that could be attributed to the study medication.
4. The subject develops symptoms or an intercurrent illness not consistent with the protocol requirements or that justify withdrawal.
5. The subject is lost to follow-up.
6. Other reasons (eg, pregnancy, development of contraindications of use of study drug as determined by the sponsor or the treating physician).
7. The study is discontinued by the sponsor or the study site.

For subjects to be considered as lost to follow-up, 2 attempts should be made to contact the subject to return for the scheduled study visit. After 2 attempts, a certified letter should be sent to the subject's address requesting the subject to contact the investigator to schedule a follow-up assessment. If no reply is provided by the subject within 30 days of receipt of the certified letter, the subject can then be considered lost to follow-up.

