⁴ PK assessments will be performed as a substudy in all sentinel subjects. For those subjects requiring dialysis, a single pre- and post-dialysis PK should be obtained for review by the DMC to decide if dose adjustment is needed. PK should be measured weekly for 2 weeks at C_{max} (4-5 hours post dose) for subjects with renal insufficiency when possible.

⁶ Assessments for clinical/respiratory status, progression, and safety serum chemistry and hematology tests to be performed and samples to be collected while hospitalized based on standard-of-care local laboratory assessments and after discharge from the hospital by home visit or outpatient clinic visit or telemedicine call. For subjects who are discharged to home or other outpatient setting after initial hospitalization, the assessments and laboratory samples can be obtained less often but not less than at least once weekly. CRP result required to determine eligibility are based on local laboratory results at screening.

⁷ Viral load testing will be collected daily for the first 4 days using central testing in the first 10 enrolled subjects as part of the sentinel safety assessment at select sites. For all subjects, including the sentinel subjects, swabs, saliva, or other sample collection (as specified in the Study Manual) for central viral load testing will be collected on D1 pretreatment and on D7 or earlier if being discharged from the hospital prior to D7.

Fulcrum Therapeutics
Protocol FIS-001-2020

Losmapimod

⁸ Vital signs will be performed after subjects have been supine for at least 5 minutes when possible. Vital signs to include oxygen saturation; PaO₂ should be recorded if available from blood gases obtained as part of SOC; oxygen administration should also be recorded (eg, room air or oxygen flow by nasal canula or facial mask or endotracheal tube). For subjects who are discharged to home or other outpatient setting after initial hospitalization, assessments may be obtained less often but at least once per week in the outpatient clinic or at home.

⁹ Height assessed at screening only; can be by self-report or from medical records. Weight is an actual recording.

¹⁰ Urinalysis will be performed during the study period only on Day 7 and on any other day only if clinically indicated.

¹¹ Pregnancy testing to be conducted within 72 hours of the first dose of study treatment.

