3.4.2 Subject withdrawal

Subjects may withdraw from the study at any time and for any reason without prejudice to their future medical care by the investigator or at the study site. In all cases of impending consent withdrawal, investigators will be given instructions to meet and discuss with the participant their options of continuing in the study. The investigator should ensure understanding and documentation of the reasons for the participant's desire to withdraw consent. Every effort should be made to keep subjects in the study, including if a subject and/or their treating physician decides to prematurely discontinue study treatment. Unless the participant provides their written withdrawal of consent or there is other written documentation by the investigator confirming the participant's verbal intent to completely withdraw from the trial, participants should be followed for all protocol-specified evaluations and assessments. The reasons for subjects not completing the study will be recorded.

A subject may be withdrawn from the study if he or she is lost to follow-up. For subjects to be considered as lost to follow-up, 2 attempts should be made to contact the subject to return for the scheduled study visit. After 2 attempts, a certified letter should be sent to the subject's address requesting the subject to contact the investigator to schedule a follow-up assessment. If no reply is provided by the subject within 30 days of receipt of the certified letter, the subject can then be considered lost to follow-up.

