6.3.1 Respiratory failure and survival assessment

Total number of study days free of oxygen supplementation and total number of study days free of respiratory failure will be evaluated. Refer to [Section 6.5.1](#) for further details of vital sign collection.

- Note: Respiratory failure is defined as either need for mechanical ventilation (invasive or non-invasive) or high flow oxygen (defined by greater than 15 LPM flow of oxygen to maintain oxygen saturation between 90% and 95%), sustained for at least 48 hours, at any time during the study.

The reason for hospitalization and number of total study days of hospitalization and intensive care unit (ICU) utilization will be recorded.

Details of subject discharge (date of discharge and condition at discharge) from the hospital will be recorded.

Any significant deviation from standard of care due to limited resources will be documented.

Survival status at the end of the study period will be documented, including cause of death for any reason.

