7.1.1 Recording of adverse events

Adverse events and SAEs will be assessed from the time the subject signs the ICF through the D28 follow-up visit.

AEs will be reported by the participant (or, when appropriate, by a caregiver, surrogate, or the participant's legally authorized representative).

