3.1.8 Handling of Dropouts and Missing Data

All missing or incomplete safety and PD data, including dates and times, will be treated as such. Missing test results or assessments will not be imputed, and as such, are assumed missing completely-at-random (MCAR).

For laboratory data, values below the limit of quantitation (recorded as “< LLQ”) will be set to half that limit.

For the analysis of hospital-free and ICU-free days, subjects who die prior to the analysis time point will have post-death days considered to be not hospital-free and not ICU-free.

Adverse events with missing start dates will be considered as treatment-emergent unless the partial date excludes that possibility, e.g., the adverse event month is prior to the first dose of study drug. Otherwise, the first day of the month will be used to impute missing start days and January will be used to impute missing start months. For example, if the first dose of study drug was on January 8, 2021 and an adverse event started in January 2021 with missing day, the start date will be imputed as the first dose date (January 8, 2021) and this adverse event will be considered as treatment-emergent. In the same example, if another adverse event has start month of December 2020 with missing day (before the first dose date of January 8, 2021), its start date will be imputed as December 1, 2020 and will not be considered as treatment-emergent.

Subjects who terminate the study prior to the analysis time point, not due to death, will be considered as missing for the analysis of key efficacy endpoints. Missing data in each treatment arm will be imputed using the observed data in their respective arm under the missing at random (MAR) assumption. Multiple imputation (MI) will be performed using the fully conditional specification (FCS) model. The imputation model will include the stratification factors, sex, and baseline CRP.

The handling of missing data for the key efficacy endpoints are outlined as the following:

1. Primary endpoint: patients whose status could not be ascertained (lost-to-follow up, etc.) will be imputed using multiple imputation approach.
2. Change in Clinical Status at Days 7 and 14: missing clinical status at the post-baseline timepoint will be imputed using multiple imputation approach.

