3.4 Efficacy Assessment

3.4.1 Primary Efficacy Endpoint

3.4.1.1 Primary Analysis

The primary efficacy endpoint is the proportion of subjects who progress to death or respiratory failure by Day 28.

Respiratory failure is defined as either need for mechanical ventilation (invasive or non-invasive) or high flow oxygen (defined by greater than 15 LPM flow of oxygen to maintain oxygen saturation between 90% and 95%), sustained for at least 48 hours, at any time during the study.

The fitted logistic regression model is used to predict the response rate for every subject in the study as if they had received the treatment or the control intervention.

Assuming p_t is probability of outcome in the losmapimod arm; p_c is the probability of outcome in the control arm

Study hypothesis: $H_0: p_t - p_c = 0$

$H_1: p_t - p_c < 0$

Assuming $p_t=0.18$, $p_c=0.30$, we can restate the hypothesis as

$H_0: \theta = \theta_0 = 0$

$H_1: \theta = \theta_1 = -0.12$

where θ is calculated as $p_t - p_c$. For the final analysis, the proportion of subjects achieving the primary endpoint in the treatment arms will be compared using an adjusted risk difference obtained from the logistic regression model, adjusted for stratification factors, sex, and baseline CRP. Sample SAS codes are provided in Appendix A. More details can be found in Guo et al. (2012) and Ge et al. (2011).

An interim analysis to assess futility analysis—and potential sample size re-estimation—will be conducted, as discussed in Section 5.1.

All results will be summarized descriptively by treatment arm and expressed as proportions, along with corresponding unadjusted/adjusted 95% CI of the difference between response rates, and p-values.

In the first step of multiple imputation, data will be multiple imputed using the FCS discriminant function separately by treatment arm to 20 imputed datasets. This analysis assumes data are missing at random. The imputation model will include the stratification factors, sex, baseline CRP, and a two-level binary factor (discharge from the hospital prior to discontinuing the study; Yes, No). [REDACTED]

For each imputed dataset, the proportion of subjects achieving the primary endpoint in the treatment arms will be compared using an adjusted risk difference obtained from the logistic regression model, adjusted for stratification factors, sex, and baseline CRP for each imputed dataset.

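### The lost-to-follow-up rule seeks an answer only from the subject, so a primary event after discharge can go unascertained and be imputed under an assumption that the event itself breaks

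*Protocol*

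**What the plan says.** **Protocol Version 3.0, section 3.4.2 (Subject withdrawal).** For a subject to be considered lost, "2 attempts should be made to contact the subject to return for the scheduled study visit". After that, "a certified letter should be sent to the subject's address requesting the subject to contact the investigator". The closing condition reads "If no reply is provided by the subject within 30 days of receipt of the certified letter". The section names no relative, representative, physician, hospital record or vital-status source.

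**SAP 3.1.8.** For the primary endpoint, "patients whose status could not be ascertained (lost-to-follow up, etc.) will be imputed using multiple imputation approach". Imputation is within arm and assumes data are missing at random (MAR). The predictors listed are the stratification factors, sex and baseline CRP.

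**SAP 3.4.1.1.** The imputation is described again, with 20 datasets, separately by arm and under MAR. The predictor list is longer here: it adds a yes/no indicator of whether the subject had been discharged before leaving the study. Text directly after this is redacted.

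**Other routes to the outcome in Protocol Version 3.0.**
- Section 6.3.1: "Survival status at the end of the study period will be documented, including cause of death for any reason".
- Section 7.1.1: adverse events may be reported, "when appropriate, by a caregiver, surrogate, or the participant's legally authorized representative".
- Table 1, general note and footnote 6: results of routine care may be taken from medical records. After discharge, assessments by home visit, clinic or telemedicine "can be obtained less often but not less than at least once weekly".

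**The concern.** The primary endpoint is death or sustained respiratory failure by Day 28. Inpatients are under observation, so loss is mainly a risk after discharge. At that stage, a subject who has died, or who is ventilated in a hospital other than the study site, cannot answer a call or a letter. The event can therefore cause the non-response. MAR imputation from baseline factors, with or without discharge status, cannot correct for that.

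The sample size text (Protocol 8.1.1) states no allowance for dropout, and section 3.4.3 does not replace withdrawals. Unascertained outcomes therefore act directly on an estimate planned to have 80% power.

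**Working it through.** **1. The planned power reproduces.** Inputs from Protocol 8.1.1, 8.6 and Table 6: p_c = 0.30, p_t = 0.18, 103 per arm at the interim, 205 per arm at the end, boundaries z = -0.67873 (futility) and z = -1.91358 (final).

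- Variance term: 0.18 x 0.82 + 0.30 x 0.70 = 0.1476 + 0.2100 = 0.3576.
- Expected z at interim: -0.12 / sqrt(0.3576/103) = -2.037.
- Expected z at final: -0.12 / sqrt(0.3576/205) = -2.873.
- Correlation: sqrt(103/205) = 0.709.
- Probability of passing both boundaries (bivariate normal, futility binding): 0.802, or 0.794 with a pooled variance. The plan states about 80%.
- Type I error is 0.0250. The probability of stopping under the null is 0.751 (stated 0.75135). Under the alternative it is 0.087-0.091 (stated 0.08871).

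**2. What hidden loss does.** Let L be the share of an arm lost after discharge, q the share of those who truly had an event, and r the rate at which they are imputed. Then:

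- observed arm rate = true rate - L(q - r)
- observed difference = -0.12 + L[(q_c - q_t) - (r_c - r_t)]

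The documents give none of L, q or r, so the values below are assumptions.

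**3. Similar loss in both arms, low imputed rate.** Take q_t = 0.6 q_c (the planned relative effect) and r = 2% in both arms. The difference becomes -0.12 + 0.4 L q_c. The table lets q_c run from 25% to 100%; the upper end is an outer limit, not an expectation.

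| L per arm | Observed difference | Power |
|---|---|---|
| 1% | -0.119 to -0.116 | 0.80 to 0.78 |
| 3% | -0.117 to -0.108 | 0.79 to 0.75 |
| 5% | -0.115 to -0.100 | 0.78 to 0.70 |
| 10% | -0.110 to -0.080 | 0.75 to 0.58 |

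Setting r to 0% or 5% changes power by about 0.01 at most. A milder case is L = 5%, q_c = 20%, q_t = 12%. The undercount is 0.05 x (0.20 - 0.02) = 0.9 points on placebo and 0.05 x (0.12 - 0.02) = 0.5 points on losmapimod. The net dilution is 0.4 of the planned 12 points, and power is about 0.78.

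**4. Higher imputed rate.** If imputation approaches the planned overall rates (30% and 18%), the same case gives 0.05 x (0.20 - 0.30) = -0.5 points on placebo and 0.05 x (0.12 - 0.18) = -0.3 points on losmapimod. Both arms are overcounted, and the difference becomes 0.183 - 0.305 = -0.122, slightly exaggerated.

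**5. Unequal loss.** Suppose there is no true effect (30% in both arms), hidden loss occurs only on losmapimod, r = 2% and q = 25-100%. The type I error rises from 0.025 to 0.028-0.041 at L = 1%, 0.035-0.096 at 3% and 0.044-0.194 at 5%. Loss only on placebo would push the estimate the other way.

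**6. Timing.** A subject missed at Day 21 cannot be classed as lost before about Day 21 + 30 = Day 51. Section 3.1 limits participation to 34 days.

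**The case against.** The strongest reply is that the protocol already provides ways to learn the outcome. Section 3.4.2 itself says that, absent documented withdrawal, participants should be followed for all specified assessments. Respiratory failure and survival are scheduled at Days 21 and 28. Contact after discharge is at least weekly and can be remote. Survival status must be documented, death is a reportable serious event, proxies may report adverse events, and medical records may be used. Being classed as lost does not in itself make the outcome missing: SAP 3.1.8 imputes only status that could not be ascertained, and a known death counts as an event. SAP 3.4.2 adds time-to-event sensitivity analyses that allow for differential follow-up.

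Much of this stands, and it makes unascertained events a risk rather than a certainty. It does not close the gap. None of these routes is a condition for declaring loss. The vital-status line does not capture ventilation elsewhere. Section 7.1.4 removes COVID-19-related hospitalization and ICU admission from the hospitalization criterion for serious events, so a readmission alone need not generate a report. The time-to-event analyses do not by themselves cure loss caused by the event. No analysis that departs from MAR is visible, although part of SAP 3.4.1.1 is redacted.

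A reader might also infer that lost subjects are always imputed at a very low rate, so that events are always undercounted. The documents do not support that. Respiratory failure counts at any time in the study, so discharged subjects with known outcome include those who had it in hospital and recovered. SAP 3.1.8 also omits the discharge factor altogether.

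The 30-day wait is not a source of bias, since it leaves more time to learn the outcome. Its fault is only that it does not fit a 28-day study.

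**Conclusion.** The point holds as a cheap improvement. Section 3.4.2 permits a subject to be declared lost on that subject's silence alone, in a trial whose primary event can cause the silence. The resulting gap is then filled under MAR.

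The size is unknown because no loss rate is given. With similar loss in both arms and a low imputed rate, the effect is diluted. Power is 0.80-0.78 at 1% lost, which is minor, and 0.78-0.70 at 5% lost, where the lower figure needs every lost placebo subject to have had an event. With unequal loss, or an imputed rate above the true one, the bias can go either way. Nothing in the double-blind plan suggests unequal loss, so the type I error figures show sensitivity and are not a forecast.

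It would be tempting to set a per-arm undercount, up to 0.10 x (0.30 - 0.02) = 2.8 points on pessimistic assumptions, beside the final boundary of 8.0 points. That comparison is not valid: the boundary applies to the difference between arms, where similar undercounts largely cancel.

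**What to change.** **Protocol 3.4.2.** Before a subject is classed as lost, require the site to seek Day 28 status (alive or dead; respiratory failure or not) from:
- a caregiver, legally authorized representative or next of kin whose details are taken at consent;
- accessible hospital or primary-physician records;
- vital-status records, where local law allows.

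State that no return visit is needed, and replace the 30-day wait with a fixed cut-off after Day 28.

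**SAP.** Reconcile the imputation predictors in 3.1.8 and 3.4.1.1, so that it is clear whether discharge status is included. Tabulate by arm the subjects whose primary status remains unascertained. The reasons for discontinuation in SAP 3.3.1 do not show this, because a subject may leave the study with a known outcome.

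**Cost.** Wording changes, one or two contact fields at consent, and a few calls or record checks. No extra visits or subjects are needed.

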3.4.3 Replacement policy

Subjects who withdraw from the study will not be replaced.

3.4.4 Stopping criteria

Dosing will be stopped in case of an unacceptable tolerability profile based on the nature, frequency, and intensity of observed AEs judged jointly by the investigator and the sponsor or as recommended by the DMC.

In the event of a study hold due to unacceptable tolerability, the sponsor will conduct an extensive safety and PK analysis and will communicate to stakeholders, including the Investigators, institutional review boards (IRBs)/independent ethics committees (IEC), and health authorities any potentially emergent safety information as well as the timing of planned resumption of dosing. Dosing and enrollment will not resume unless it is considered safe to do so after consultation with Investigators and health authorities and approval by IRBs/IECs.

Fulcrum Therapeutics
Protocol FIS-001-2020

Losmapimod

4 STUDY POPULATION

4.1 Inclusion criteria

Eligible subjects must meet all of the following inclusion criteria at screening.

1. Able and willing to provide written informed consent.
2. Willing and able to comply with all study procedures.
3. Age ≥ 50 years at time of screening.
4. Confirmed infection with SARS-CoV-2 virus at or before the baseline visit (by polymerase chain reaction [PCR] testing).
 - a. Note: Refer to the Study Manual for details on PCR SARS-CoV-2 testing procedures.
5. ≤ 7 days to the time of randomization from the time of collection of the specimen that tested positive for the SARS-CoV-2 virus.
6. Hospitalization at the time of the baseline visit.
7. $\geq 90\%$ oxygen saturation on room air and/or $\geq 94\%$ oxygen saturation on oxygen administration at 2 L/min by nasal canula at the baseline visit.
8. Radiographic (X-ray or computed tomography scan, per local standard of care) evidence of pulmonary involvement consistent with COVID-19 at screening or baseline, per the judgment of the investigator.
 - a. Note: If radiography is not considered local standard of care for COVID-19 diagnosis, evidence of pulmonary involvement consistent with COVID-19 may also be obtained from clinical examination, per the judgment of the investigator. Evidence of pulmonary involvement obtained by clinical examination should be documented in the eCRF.
9. Clinical syndrome consistent with COVID-19 at screening, per the judgment of the investigator ([CDC 2020](#)).
10. CRP at screening >15 mg/L on local laboratory testing.
11. Agrees to practice an approved method of birth control as follows:
 - a. Females of childbearing potential: Using 1 of the following acceptable methods of contraception: surgical sterilization (eg, bilateral tubal ligation), intrauterine contraception/device, hormonal contraception, or any 2 barrier methods (a combination of male or female condom with diaphragm, sponge, or cervical cap). This criterion must be followed from the time of the first dose of study medication until 90 days after last dose
 - b. Males: Effective male contraception includes a vasectomy with negative semen analysis at follow-up, or the use of condoms. This criterion must be followed from the time of the first dose of study medication until 90 days after last dose.

Note: Abstinence can be considered an acceptable method of contraception at the discretion of the investigator. Periodic abstinence (eg, calendar, ovulation, symptothermal, post ovulation methods) and withdrawal are not considered acceptable methods of contraception.

Fulcrum Therapeutics
Protocol FIS-001-2020

Losmapimod

